## 11.0 TOXICITIES/SIDE EFFECTS

No acute side effects are expected as a result of this study. However, in the unlikely event that an adverse reaction to either radiopharmaceutical occurs, the results must be documented and reported by the Principal Investigator to both the Institutional Review Board, and the Investigative New Drug Committee.

To ensure patient safety, vital signs and toxicity assessments will be performed immediately after each scan session. Additionally, approximately 24 hours (or on the next business day) after the completion of each scan session, a toxicity assessment will be completed via a telephone followup.

The risks of this study include exposure to unnecessary radiation. This risk will be clearly outlined in the informed consent.

Adverse Events will be graded using the NCI Common Terminology Criteria for Adverse Events- Version 4.0.

Information about both diagnostic agents, F-FDG and FMISO, and the corresponding dosimetry tables are summarized below.

## **11.1 F-FDG PET Scan**

### **11.1.1 F-FDG PET Schedule**

F-FDG is an FDA approved radiotracer. In patients who are receiving radiation and agree to participate in this protocol, one additional F-FDG PET scan will be obtained mid-treatment (as described in section 1.0) to assess response to therapy. This follow up FDG scan is investigational. Besides, in the baseline FDG PET/CT, which is standard of care, additional two one PET/CT FOV over the lesion will be acquired following the clinical scan. This additional FOV is investigational and will be acquired first in FB and then in BH (same as for the investigational follow up FDG PET/CT study). The CT components will be acquired in cine mode and then BH respectively.

Only patients in Group 1 will participate in BH scans.

### **11.1.2 F-FDG Production**

All F-FDG doses will be purchased from IBA.

### **11.1.3 Dosimetry Estimates for F-FDG**

Table 3 below summarizes normal organ doses due to F-FDG administration.

Target Organ	Median Dose (rad/mCi)	Absorbed Doses	
		Follow Up FDG PET/CT	0.903 rad (*) + Dose (rad) per 12mCi FDG
Adrenals	0.052	0.624	0.624
Bone Surfaces	0.037	0.444	0.444
Brain	0.17	2.04	2.04
Gall Bladder Wall	0.088	1.056	1.056
Heart Wall	0.25	3.903	4.74
Kidneys	0.078	0.936	0.936
Large Intestine - Lower Wall	0.059	0.708	0.708
Large Intestine - Upeer Wall	0.048	0.576	0.576
Lens of Eye	0.041	0.492	0.492
Liver	0.088	1.056	1.056
Lungs	0.0028	0.9366	1.7736
Muscle / Other Tissue	0.041	0.492	0.492
Pancreas	0.052	0.624	0.624
Red Marrow	0.041	1.395	2.232
Small Intestine	0.048	0.576	0.576
Stomach Wall	0.044	0.528	0.528
Testes	0.056	0.672	0.672
Thyroid	0.012	0.144	0.144
Total Body	0.043	0.516	0.516
Urinary Bladder Wall			
45 min Voiding Interval	0.165	1.98	1.98
1 hr Voiding Interval	0.22	2.64	2.64
1.5 hrs Voiding Interval	0.34	4.08	4.08
2 hr Voiding Interval	0.44	5.28	5.28
Effective Dose Equivalent (rem)	0.1	1.46187	1.7046

(\*) Cumulative CT dose from FB-CT (0.066 rad), BH-CT (0.066 rad), and 4D-CT (0.771 rad) (Total = 0.903 rad)

(\*\*) Cumulative CT dose from BH-CT (0.066 rad) and 4D-CT (0.771 rad) (Total = 0.837 rad)

(1) FDG Package Insert, Eastern Isotopes, Inc, Asbnun, VA, 1998.

(2) Wu et al. Eur J Nucl Mol Imaging 31:38-43, 2004.

Table 3.

The organ receiving highest radiation dose from the investigational F-FDG scan is the heart wall ( 3.0 rad ). Additional doses of 0.066 rad from the FB CT, 0.771 rad from one 4D-CT scans (avg CT) and 0.066 rad from a BH-CT will be delivered to the patient. The total dose to the heart wall from the investigational F-FDG scan is 4.74 rad.

## 11.2 F-FMISO PET Scan

### 11.2.1 F-FMISO PET Schedule

F-FMISO is a radiotracer which MSKCC holds an approved IND. In patients who agree to participate in this protocol, two F-FMISO PET Scans will be obtained within 5 days, at least 1 day after the baseline F-FDG-PET that is required as part of pretreatment enrollment criteria.

### 11.2.2 $^{18}\text{F}$ -FMISO Production

$^{18}\text{F}$ -fluoride is produced by the Memorial Sloan-Kettering Cancer Center cyclotron by proton irradiation of an enriched O-18 water target in a small-volume titanium chamber.  $^{18}\text{F}$ - FMISO is prepared at an approximate specific activity of  $2.5 \times 10^7 \text{ MBq}/\text{mmol}$  at production time. Patients will be injected with a maximum of  $10 \pm 10\%$  mCi of  $^{18}\text{F}$ -FMISO on each of the 2  $^{18}\text{F}$ -FMISO scan days.

### 11.2.3 Dosimetry Estimates for $^{18}\text{F}$ -FMISO

Bio-distribution data has been obtained for 25 patients at the University of Washington, and dosimetry was performed. Table 4 below summarizes normal organ doses due to  $^{18}\text{F}$ - FMISO administration.

F18-FMISO Patient Dosimetry			
Target Organ	Absorbed Doses		
	Median Dose (rad/mCi)	2.51 rad (*) + Dose (rad) per 10mCi FMISO	2x2.51 rad (*) + Dose (rad) per 2x10mCi FMISO
Adrenals	0.0614	0.614	1.228
Brain	0.0318	0.318	0.636
Breasts	0.0455	0.455	0.91
Heart Wall	0.0685	3.195	6.39
Stomach	0.0466	0.466	0.932
Kidney	0.0581	0.581	1.162
Liver	0.0677	0.677	1.354
Lungs	0.0366	2.876	5.752
Muscle	0.0525	0.525	1.05
Ovaries	0.0651	0.651	1.302
Red Marrow	0.0403	2.913	5.826
Spleen	0.0603	0.603	1.206
Thyroid	0.0559	0.559	1.118
Eye Lens	0.057	0.57	1.14
Total Body	0.0466	0.466	0.932
Urinary Bladder Wall			
45 min Voiding Interval	0.0291	0.291	0.582
1 hr Voiding Interval	0.0389	0.389	0.778
1.5 hrs Voiding Interval	0.0583	0.583	1.166
2 hr Voiding Interval	0.0777	0.777	1.554
Uterus	0.0677	0.677	1.354
Effective Dose Equivalent (rem)	0.0481	0.481	0.962

Table 4.

The organ receiving highest radiation dose from the two  $^{18}\text{F}$ -FMISO scans is the heart wall (  $2 \times 0.685 \text{ rad}$  ). Additional doses from 6 BH-CT scans (3 BH-CT per  $^{18}\text{F}$ -FMISO study) of  $0.396 \text{ rad}$  ( $6 \times 0.066 \text{ rad}$  ), and six 4D-CT scans (avg CT) (three 4D-CT per  $^{18}\text{F}$ -FMISO study) of  $4.626 \text{ rad}$  ( $6 \times 0.771 \text{ rad}$  ) for a total of  $2.51 \text{ rad}$  per  $^{18}\text{F}$ -FMISO study or  $5.02 \text{ rad}$  for both  $^{18}\text{F}$ -FMISO studies.

FMISO studies, will be delivered to the patient bringing the total radiation dose to the heart wall to 6.39 rad.

#### **11.2.4 Dosimetry Estimates for simultaneous $^{18}\text{F}$ -FMISO/ $^{18}\text{F}$ -FDG**

Based on the dosimetry data of tables 1 and 2, dosimetry was performed. Table 5 below summarizes normal organ doses due to simultaneous  $^{18}\text{F}$ -FMISO/ $^{18}\text{F}$ -FDG administration.

Target Organ	Absorbed Doses		
	Dual FDG/FMISO		
	Dose (rad) per 8mCi FDG	Dose (rad) per 8mCi FMISO	0.198rad + 2.313 rad + Dose (rad) per 8mCi FMISO + per 8mCi FDG
Adrenals	0.416	0.491	0.907
Bone Surfaces	0.296	0.228	0.524
Brain	1.36	0.254	1.614
Gall Bladder Wall	0.704	0.438	1.142
Heart Wall	2	0.548	5.059
Kidneys	0.624	0.465	1.089
Large Intestine - Lower Wall	0.472	0.423	0.895
Large Intestine - Upeer Wall	0.384	0.414	0.798
Lens of Eye	0.328	0.456	0.784
Liver	0.704	0.542	1.246
Lungs	0.0224	0.293	2.826
Muscle / Other Tissue	0.328	0.420	0.748
Pancreas	0.416	0.530	0.946
Red Marrow	0.328	0.322	3.161
Small Intestine	0.384	0.390	0.774
Stomach Wall	0.352	0.373	0.725
Testes	0.448	0.432	0.880
Thyroid	0.096	0.447	0.543
Total Body	0.344	0.373	0.717
Urinary Bladdr Wall			
45 min Voiding Interval	1.32	0.233	1.553
1 hr Voiding Interval	1.76	0.311	2.071
1.5 hrs Voiding Interval	2.72	0.466	3.186
2 hr Voiding Interval	3.52	0.622	4.142
Effective Dose Equivalent (rem)	0.8	0.385	1.185

(1) FDG Package Insert, Eastern Isotopes, Inc, Asbnun, VA, 1998.

(2) Wu et al. Eur J Nucl Mol Imaging 31:38-43, 2004.

Table 5.

The organ receiving highest radiation dose from the combined FMISO/FDG scan is the heart wall (2.548 rad). Additional doses from 3 BH-CT scans (3 BH-CT per F-FMISO study) of 0.198 rad (3 x

0.066 rad), and three 4D-CT scans (avg CT) (three 4D-CT per F-FMISO study) of 2.313 rad (3 x 0.771 rad), bringing the total dose to the heart to 5.059 rad per FMISO/FDG study.

### 11.2.5 Total Doses from All Studies

Based on the dosimetry data of tables 1 and 2, dosimetry was performed. Table 6 below summarizes the total normal organ doses from the FDG PET/CT, 2xFMISO PET/CT, and combined FMISO/FDG PET/CT.

Target Organ	Absorbed Doses			
	Total Dose from All FDG and FMISO studies (including the corresponding CT-BH's and 4DCT's)			
	0.903 rad (*) + 0.837 rad (**) Dose (rad) per 12mCi FDG	2x2.51 rad (*) + Dose (rad) per 2x10mCi FMISO	0.198rad + 2.313 rad + Dose (rad) per 8mCi FMISO + per 8mCi FDG	Total Dose
Adrenals	0.624	1.228	0.907	2.759
Bone Surfaces	0.444	0.57	0.524	1.538
Brain	2.04	0.636	1.614	4.290
Gall Bladder Wall	1.056	1.095	1.142	3.293
Heart Wall	4.74	6.39	5.059	16.189
Kidneys	0.936	1.162	1.089	3.187
Large Intestine - Lower Wall	0.708	1.0575	0.895	2.661
Large Intestine - Uperer Wall	0.576	1.035	0.798	2.409
Lens of Eye	0.492	1.14	0.784	2.416
Liver	1.056	1.354	1.246	3.656
Lungs	1.7736	5.752	2.826	10.352
Muscle / Other Tissue	0.492	1.05	0.748	2.290
Pancreas	0.624	1.325	0.946	2.895
Red Marrow	2.232	5.826	3.161	11.219
Small Intestine	0.576	0.975	0.774	2.325
Stomach Wall	0.528	0.932	0.725	2.185
Testes	0.672	1.08	0.880	2.632
Thyroid	0.144	1.118	0.543	1.805
Total Body	0.516	0.932	0.717	2.165
Urinary Bladder Wall				
45 min Voiding Interval	1.98	0.582	1.553	4.115
1 hr Voiding Interval	2.64	0.778	2.071	5.489
1.5 hrs Voiding Interval	4.08	1.166	3.186	8.432
2 hr Voiding Interval	5.28	1.554	4.142	10.976
Effective Dose Equivalent (rem)	1.2	0.962	1.185	3.347

(1) FDG Package Insert, Eastern Isotopes, Inc, Asbnun, VA, 1998.

(2) Wu et al. Eur J Nucl Mol Imaging 31:38-43, 2004.

Table 6.

The organ receiving the highest radiation dose in the case of the five patients that will undergo the combined FMISO/FDG study is the heart at 16.189 rad. This is based on the doses from the mid-treatment FDG scan, the baseline and follow up FMISO scan, the combined FMISO/FDG scan, and all the corresponding CT's.

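### The all-study effective dose in Table 6 (3.347 rem) leaves out CT under a heading that says CT is included, and conflicts with Table 3 for the same FDG exposure

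*Combined protocol and SAP*

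**What the plan says.** Section 11.0 names radiation as a risk of taking part: "The risks of this study include exposure to unnecessary radiation". Sections 11.1.3 to 11.2.5 then tabulate organ doses and an effective dose equivalent.

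- **Table 3 (FDG, section 11.1.3)** gives 0.1 rem per mCi, then 1.46187 and 1.7046 rem. Its footnotes list two CT sets, one of 0.903 rad and a second described as "Cumulative CT dose from BH-CT (0.066 rad) and 4D-CT (0.771 rad) (Total = 0.837 rad").
- **Table 4 (two FMISO studies, section 11.2.3)** gives 0.481 and 0.962 rem under column headings that add 2.51 rad of CT per study. The text counts the CTs: "Additional doses from 6 BH-CT scans (3 BH-CT per" study), with six 4D-CTs.
- **Table 5 (dual-tracer study, section 11.2.4)** gives 1.185 rem under a heading that lists 0.198 + 2.313 rad of CT. Its text begins the CT count with "Additional doses from 3 BH-CT scans (3 BH-CT per" study).
- **Table 6 (all studies, section 11.2.5)** is headed "Total Dose from All FDG and FMISO studies (including the corresponding" breath-hold and 4D CTs). Its effective-dose row reads 1.2, 0.962, 1.185, total 3.347 rem.

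On the heart dose, section 11.1.3 itemises the investigational FDG scan as 3.0 rad from tracer plus "Additional doses of 0.066 rad from the FB CT, 0.771 rad from one 4D-CT scans (avg CT) and 0.066 rad from a BH-CT". It then says the total for that "scan is 4.74 rad". Section 11.2.5 explains its heart total of 16.189 rad as follows: "This is based on the doses from the mid-treatment FDG scan, the baseline and follow up FMISO scan, the combined FMISO/FDG scan" and the associated CTs.

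Sections 9.1, 9.2 and 11.1.1 restrict breath-hold scans to Group 1. Section 9.4, which governs the Group 2 dual-tracer study, calls for a breath-hold CT at each imaging session.

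**The concern.** The effective-dose row appears to change meaning between tables without a label. A reader of Table 3 sees CT included. A reader of Table 6 is told by the heading that CT is included, yet sees a smaller number for the same FDG exposure.

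Table 6 holds the protocol's only effective-dose figure for all the studies together. An ethics committee or consent writer who takes it at face value would understate the exposure on the table's own terms.

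Two statements behind the tables raise related doubts. The listed components of the FDG heart dose do not add up to the stated total, and the text disagrees on whether Group 2 has breath-hold scans at all.

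**Working it through.** **Inputs.** FDG 0.1 rem/mCi at 12 mCi (Table 3) and 8 mCi (Table 5). FMISO 0.0481 rem/mCi at 2 × 10 mCi (Table 4) and 8 mCi (Table 5). CT: 0.903 and 0.837 rad (Table 3 footnotes), 5.02 rad for two FMISO studies (section 11.2.3), and 0.198 + 2.313 = 2.511 rad for the dual study (Table 5).

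**1. Reproduce the Table 6 total with tracer only.**
- FDG: 12 × 0.1 = 1.2
- Two FMISO studies: 20 × 0.0481 = 0.962
- Dual study: 8 × 0.1 + 8 × 0.0481 = 1.1848, printed as 1.185
- Sum: 1.2 + 0.962 + 1.185 = 3.347 rem, exactly as printed, with no CT.

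**2. Decompose Table 3's effective-dose row.**
- (1.46187 − 1.2) / 0.903 = 0.290
- (1.7046 − 1.2) / (0.903 + 0.837) = 0.5046 / 1.740 = 0.290

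The same factor comes out of both cells, so Table 3 includes a weighted CT term.

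**3. Check that Table 3's last column and Table 6's first column describe the same exposure.** Tracer plus 1.740 rad of CT gives:

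| Organ | Tracer (12 mCi FDG) | + 1.740 rad CT | Table 3 | Table 6 |
|---|---|---|---|---|
| Heart wall | 3.0 | 4.74 | 4.74 | 4.74 |
| Lungs | 0.0336 | 1.7736 | 1.7736 | 1.7736 |
| Red marrow | 0.492 | 2.232 | 2.232 | 2.232 |
| Effective dose (rem) | 1.2 | 1.7046 (at 0.29) | 1.7046 | **1.2** |

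The three organ rows agree; the effective-dose row does not.

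**4. CT carried in Table 6's totals (printed total minus tracer dose).** Heart, lungs and marrow each carry 9.271 rad, which equals 1.740 + 5.02 + 2.511. Total Body carries none: 0.516 + 0.932 + 0.717 = 2.165, as printed. The effective-dose row also carries none.

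**5. Size from printed figures.** Replacing only the FDG entry with Table 3's value: 1.7046 + 0.962 + 1.185 = 3.852 rem (3.852 / 3.347 = 1.15). If the FDG entry means the mid-treatment scan alone: 1.46187 + 0.962 + 1.185 = 3.609 rem (1.08-fold). Both sums mix a CT-inclusive entry with two tracer-only entries, so neither is a corrected total.

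**6. Size with CT throughout (assumption).** The documents state no CT factor f. The total is 3.347 + f × 9.271; on the single-scan reading the CT is 9.271 − 0.837 = 8.434 rad.

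| Assumed f (rem/rad) | All CT in Table 6 (rem) | Single FDG scan reading (rem) |
|---|---|---|
| 0.12 | 4.46 | 4.36 |
| 0.20 | 5.20 | 5.03 |
| 0.29 (implied by Table 3) | 6.04 | 5.79 |
| 0.40 | 7.06 | 6.72 |

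**7. FDG heart dose.** The listed items give 3.0 + 0.066 + 0.771 + 0.066 = 3.903 rad, against 4.74 stated. The gap, 4.74 − 3.903 = 0.837 rad, is exactly the second CT set in the Table 3 footnotes. If only the mid-treatment FDG scan is meant, as section 11.2.5 says, the heart total is 3.903 + 6.39 + 5.059 = 15.352 rad instead of 16.189.

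**8. Breath-hold scans.** Sections 9.1, 9.2 and 11.1.1 confine them to Group 1. Section 9.4 requires a breath-hold CT at each session of the Group 2 dual study, and Table 5 counts three at 0.066 rad each.

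**The case against.** The best defence is that the tables follow a local-field convention: CT is added only to heart, lungs and marrow, and every other organ row is tracer-only under the same headings. Three of the four tables treat effective dose the same way, so Table 3 may be the outlier and 3.347 rem a sound tracer-only figure with a loose heading. This stands as far as it goes: the documents do not settle which convention was intended. It does not remove the contradiction, because Table 3 adds a weighted CT term to this very row and Table 6 does not.

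Three further objections have some force.

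- The 0.29 factor is inferred from two cells of one table, and the other factors have no source in the documents. The 4.5 to 7.1 rem range shows sensitivity; it does not estimate the error.
- Table 3's last column heading, as extracted, shows only 0.903 rad. That it matches Table 6's exposure is inferred from the organ values, but three exact matches make the inference secure.
- The 4.74 rad heart figure can be rebuilt as 3.0 + 0.903 + 0.837. Table 6's heading lists both CT sets, and section 11.1.1 describes extra research imaging at baseline. The fault is therefore incomplete prose in sections 11.1.3 and 11.2.5, with no arithmetic error in the heart row.

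The breath-hold restriction might be meant for PET only; the text does not say so. It is a separate matter from the effective-dose convention, though it bears on what Table 5 counts.

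**Conclusion.** The point holds, as a minor one. The printed cells alone show that the effective-dose row includes CT in Table 3 and excludes it in Tables 4 to 6, and that the 3.347 rem total contains none despite its heading. No assumption is needed for that.

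The size of a consistent CT-inclusive total does need one: about 6.0 rem if Table 3's implied factor applies to all the CTs, or about 5.8 rem if the FDG entry is the mid-treatment scan alone.

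The consequences are limited. Table 6 applies to at most the five dual-study patients, although Table 4's tracer-only entries also describe Group 1's FMISO scans. No endpoint, sample size or analysis is affected, and the heart dose quoted in the text already includes CT. The consent form is not among the documents, so it cannot be known which figure patients were given.

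**What to change.** Use one CT convention for the effective-dose row in Tables 3 to 6 and state it in a footnote. There are two ways to do this:

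- Recompute the row in Tables 4, 5 and 6 with CT included, and give the conversion factor and its source.
- Label the row tracer-only, correct Table 3 and the Table 6 heading, and report the CT contribution separately.

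In section 11.1.3, reconcile the itemised 3.903 rad with the stated 4.74 rad. In section 11.2.5, say whether the FDG entry covers the mid-treatment scan only or also the baseline research CT. Reconcile the Group 1 restriction on breath-hold scans in sections 9.1, 9.2 and 11.1.1 with section 9.4 and Table 5.

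The cost is one recalculated or relabelled row, a footnote and a few corrected sentences. If CT is included, the stated exposure becomes less favourable. No change to any activity, scan or schedule is proposed.

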## **12.0 CRITERIA FOR THERAPEUTIC RESPONSE/OUTCOME ASSESSMENT**

There are two primary goals for this study; first, to assess the reproducibility of kinetic analysis of dynamic  $^{18}\text{F}$ -FMISO PET images, in both BH and FB data sets, and second, to assess the prognostic value of hypoxia, as measured with  $^{18}\text{F}$ -FMISO PET, with OS and PFS in NSCLC. As explained above, the presence and extent of tumor hypoxia will be measured by means of kinetic analysis of dynamic  $^{18}\text{F}$ -FMISO PET images. Kinetic analysis parameters may be susceptible to breathing-induced motion artifacts due to patient respiration. Hence, the correlation of outcome to both the presence and extent of tumor hypoxia may be inaccurate. We will therefore conduct analyses based on BH- and FB- PET datasets, and then compare the results in order to assess the effect breathing on these parameters. This exploratory objective of tumor hypoxia correlation to clinical endpoints is dependent on time to tumor progression and death. We will follow up with these patients up to a maximum of three years. The table below summarizes the milestones of this research project.

Likewise, the predictive value of FDG PET may also be suspect due to breathing motion artifacts. In light of the discussion above, therefore, the secondary aim is to compare the predictive value of FDG PET when the data are acquired in BH versus in FB PET.

## **13.0 CRITERIA FOR REMOVAL FROM STUDY**

If at any time the patient develops unacceptable toxicity he/she will be removed from study. An unacceptable toxicity will be defined by a grade III/IV toxicity requiring hospitalization as per CTCAE v4.0

If at any time the patient is found to be ineligible for the protocol as designated in the section on Criteria for Patient/Subject Eligibility (i.e., a change in diagnosis), the patient will be removed from the study.

Patients who are withdrawn from the study before completing all protocol required scans will be replaced to ensure there are 25 evaluable patients.

## **14.0 BIOSTATISTICS**

This study will enroll 25 patients with non-small cell lung cancer (NSCLC) who will undergo treatment with definitive conventionally fractionated radiation therapy (RT), neoadjuvant chemotherapy, or chemo-RT. In addition to standard of care PET/CT scans, they will also be scanned twice at baseline (pre-treatment) with experimental  $^{18}\text{F}$ -FMISO scans.

Since some patients will have multiple lesions some of the statistical analyses will be lesion-based and some will be patient-based. This is explained in detail within each analysis but primarily, reproducibility analyses will be lesion-based and analysis of predictive values will be patient-based. Presence and extent of hypoxia will be analyzed twice, one lesion-based and the other patient-based. One of the primary objectives is to evaluate the reproducibility of kinetic analysis in serial, BH and Free-Breathing (FB), dynamic  $^{18}\text{F}$ -FMISO PET images. Hypoxia is measured by  $k_3$ , the trapping rate (see section 7.3). This will be analyzed both as a binary and a continuous variable: if any of the voxels

inside the tumor has a  $k3 > 0.1$  the tumor is defined to be hypoxic while its extent will be defined by the fraction of hypoxic volume which is the fraction of tumor volume with  $k3 > 0.1$ . Reproducibility will be evaluated using Cohen's kappa for presence of hypoxia and concordance correlation coefficient for the extent of hypoxia. This will be a lesion-based analysis and multiple observations per patient will be taken into account using a variance inflation factor estimated from the intraclass correlation coefficient.

Another primary objective is to compare the presence and extent of hypoxia with the clinical outcome (see section 7.3 and above for the definition of hypoxia). Previous studies showed comparable outcomes for stage IIIA (which is the majority treated) when following either of the two treatment arms considered in this study (51, 52).

Therefore, data from both groups of patients will be analyzed together. Historical data suggests 38% of patients will be free of recurrence at 3 years (53), which provides us with approximately 80% power to detect a hazard ratio of 3.0 between groups of low and high change. This calculation is based on a log-rank test and assumes that extent of hypoxia is dichotomized at observed median resulting in equal group sizes and maximal power. This is for planning purposes only. We will use Cox regression with extent of hypoxia as the covariate in two different ways: (1) lesion-based analysis with an estimating equations to account for multiple observations per patient; (2) patient-based where an aggregate measure of extent of hypoxia (sum of the fraction of tumor volumes with  $k3 > 0.1$  across all lesions) over all lesions within a patient) will be used as a covariate. In addition, a lesion and patient-based analyses for presence of hypoxia will also be considered where, for the patient-based analysis, the aggregate measure will be defined as presence of hypoxia in at least one of the lesions.

In an exploratory analysis to address the secondary objective of assessing the predictive value of FDG PET/CT in a group of twenty five lung cancer patients undergoing radiotherapy or concurrent chemoradiotherapy, we will use the concordance probability estimate from a proportional hazards regression model with SUV as the predictor for the outcomes of survival and progression-free survival. Time of origin will be the start time of therapy (neoadjuvant therapy, if applicable, concurrent chemoradiation or radiation alone otherwise). We will use these estimates to preliminarily determine whether BH PET/CT provides greater predictive capability than Free-Breathing (FB) PET/CT. Since these analyses are exploratory findings will be interpreted as hypothesis-generating.

We expect to accrue one patient a month for each of the two cohorts.

